- a. the effects in sedentary men and women of two primary-care based activity counseling regimens (B and C, representing the staff-assisted and staff-counseling interventions, respectively) on physical activity (defined as energy expenditure) ($\text{kcal}\cdot\text{kg}^{-1}\cdot\text{day}^{-1}$) after 24 months when compared to a Standard Care control (Group A) and to each other; and
- b. the effects in sedentary men and women of the two primary-care based activity counseling regimens (B and C) on cardiorespiratory endurance (defined as maximum oxygen consumption or $\text{VO}_{2\text{max}}$) ($\text{L}\cdot\text{min}^{-1}$) after 24 months when compared to Standard Care control and to each other.

2. Secondary Objectives

Although the primary purpose of ACT is to increase physical activity and cardiorespiratory endurance, a variety of secondary outcomes are important for assessing the effects of the interventions. These include short-term intervention effects, alternate measures of physical activity and fitness, levels of factors related to cardiovascular disease risk, psychosocial factors, and cost-effectiveness. These outcomes may be important for medical care practices to assess their relative enthusiasm for implementing physical activity intervention programs for their patients. In addition, intervention effects in different types of participants are important to assess. The interventions may be successful in some groups but not in others for a variety of reasons such as different perceptions, needs, abilities, or cultural factors.

Secondary objectives are to compare the relative effectiveness of the two primary-care based counseling regimens (Interventions B and C) to each other and vs. Standard Care (Group A) control on:

- a. the effects on physical activity and cardiorespiratory endurance after 6 months;
- b. the effects on submaximal treadmill test performance and shifts from sedentary to light and moderate activity after 6 and 24 months;
- c. the effects on factors related to cardiovascular disease risk (HDL-cholesterol, LDL-cholesterol, total cholesterol, triglycerides, blood pressure, plasma insulin, fibrinogen, body composition, dietary fat intake, smoking status, and heart rate variability) after 6 and 24 months;
- d. the effects on psychosocial factors (mood, self-efficacy, quality of life) after 6 and 24 months;
- e. the relative cost-effectiveness of the two regimens after 24 months;

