5. STATISTICAL CONSIDERATIONS

5.A Primary Analyses

Two primary (null) hypotheses have been defined for testing in ACT:

- H₁: there are no differences among the mean levels of VO₂max among persons randomized to the three groups of the clinical trial at 24 months post-randomization, and
- H₂: there are no differences among the mean levels of seven-day self-reported physical activity levels among persons randomized to the three groups of the clinical trial at 24 months post-randomization.

Each hypothesis will be tested according to the intention-to-treat philosophy (Friedman, 1985) in which all randomized participants will be grouped according to their intervention assignment at randomization, regardless of compliance. All primary comparisons will be two-sided (Fleiss, 1987). A Bonferroni adjustment for multiple comparisons will be used to control the Type I error across the two primary hypotheses: individually, each hypothesis will be tested at significance level 0.025. Separate hypothesis tests will be performed on women and men.

General linear models will be used to model the serial data collected on each primary outcome measure. Time since randomization will be grouped by targeted exams (i.e. 6 or 24 month) and parameterized as a fixed class effect. The primary hypotheses will be tested using linear contrasts for interactions between treatment assignment and the indicator variable for the 24 month exam. No *a priori* parametric structure will be assumed for serial correlation. The baseline level of the measure (i.e. VO₂max or seven-day physical activity recall) will be included as a covariate in models, as will terms for the stratification factors: clinical center and race (African-American, Hispanic, Other).

Extensive attempts are planned to promote the retention of ACT participants; however it is expected that not all randomized participants will be evaluated at 24 months. Including interim

data on VO₂max and seven-day physical activity in analyses testing the 24-month differences is expected to reduce the potential biases that may be associated with missing data. This approach allows all participants who have post-randomization measures to contribute to the analysis, and therefore does not exclude persons who are missing 24-month data.

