Secondary analyses will be performed to explore the effect that assumptions about missing data have on trial results. Sensitivity analyses will be conducted in which analysis of results will be performed based on 1) assuming the missing data are missing at random, conditioned on the value of covariates and intermediate results, and 2) assuming that all the unobserved missing data in the intervention and control groups have the same distribution as the observed data in the control group. If these analyses indicate that the results differ substantially, depending on the assumptions one makes about the missing data mechanism, further analyses involving model-based alternatives to the planned primary analyses (e.g. Schluchter, 1992; Shih, 1992; Diggle and Kenward, 1994) and post-hoc stratification (e.g. D'Agostino, 1994) will be explored.

Based on analyses from the Stanford-Sunnyvale Health Improvement Project (SSHIP-I) trial, VO₂max measurements are anticipated to have a right-skewed distribution with the variance increasing with the mean; if this pattern emerges in ACT, a logarithmic transformation will be used, as in the sample size calculations presented below. Each of the three pairwise comparisons of the intervention groups will be tested using a Bonferroni-adjusted significance level of $\alpha=0.0083$ (0.025/3), as is specified in the sample size calculations.

5.B. Secondary Analyses

A series of publications based on the baseline data will be developed to provide the investigators with a first opportunity for a systematic exploration of the central databases; to assist in developing definitions of new variables for future analyses; to begin the development of scientific collaborations; and to cement the protocol for trial publications. Baseline analyses will include descriptions of recruitment, the baseline characteristics of the participants, and cross-sectional analyses of relationships among study variables.

Although the primary hypotheses only address 24-month change, it will be important to examine how the interventions may affect VO₂max and seven-day physical activity recall across the full 24 month period. Secondary analyses will be performed to track these measures across time using mixed effects analysis of covariance models to allow for both time-varying changes in covariates, and varying covariance structures (Laird and Ware, 1982; Jennrich and Schluchter, 1986; Diggle, 1988; Laird, 1992; Wolfinger, 1992).

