Sample size calculations for the ACT trial were based on recruitment of an equal number of participants to each of its three groups. The two primary outcomes in these calculations are logarithmic-transformed VO₂max measurements (unadjusted for weight) and total kilocalorie expenditure per kilogram body weight by seven-day physical activity recall, including light, moderate and heavy activities, but not including sleep. For each primary outcome, the hypotheses to be tested will investigate 24-month differences between all intervention groups; thus a total of six pairwise comparisons will be performed. Preliminary data used for estimating standard deviations of outcomes were obtained from the SSHIP-I trial run by investigators at Stanford University. Based on the SSHIP-I information, we estimated that the standard deviations of log transformed, 24-month VO₂max measurements adjusted for baseline measurements were 0.1214 for men and 0.1215 for women, respectively. Standard deviations for total kilocalorie expenditure were only available for 12 months of follow-up. The 12-month standard deviations of total kilocalorie expenditure were 2.0894 for men and 2.0206 for women, after adjustment for baseline measurements. Sample size calculations were performed separately for men and women.

To ensure an overall, two-sided, Type I error rate, α , of 0.05, each pairwise comparison will be performed at the 0.0083 level (0.05/6), thus using critical regions containing 0.00417 probability in each tail. Assuming equal variances of 24-month outcomes for all intervention groups, the general formula used to determine the appropriate sample size to detect a difference of δ with $1-\beta$ power is

$$N = \left(\frac{1}{r} \right) V \left(\frac{1}{P_1} + \frac{1}{P_2} \right) \frac{(Z_{1-\alpha/2/m} + Z_{1-\beta})^2}{\delta^2},$$

where r is the proportion of participants that will not be lost to follow-up prior to 24 months, V is the baseline adjusted variance of the outcome variable, P_1 and P_2 are the proportion of subjects in the groups being compared, m is the number of trial groups times the number of primary outcomes, and $Z_{1-\alpha/2/m}$ and $Z_{1-\beta}$ are percentiles from a standard normal distribution. For the calculations reported below, we assume 20% loss to follow-up ($r = 0.8$) and have allowed equal numbers in each group. $Z_{1-\alpha/2/6} = Z_{0.00417} = 2.64$ and, for 90% power, $Z_{1-0.1} = 1.282$.

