The sample size of the trial is based on being able to detect a 7% difference in VO_{2max} and a $1.1 \text{ kcal} \cdot \text{kg}^{-1} \cdot \text{day}^{-1}$ difference in total energy expenditure with 90% power. The 7% difference would equal a difference of $2000 \text{ ml} \cdot \text{min}^{-1}$ versus $1869 \text{ ml} \cdot \text{min}^{-1}$. The goal of the intervention groups is to target an increase in energy expenditure equal to approximately $2 \text{ kcal} \cdot \text{kg}^{-1} \cdot \text{day}^{-1}$. The trial is designed to detect an intervention that would obtain this increase on some but not all participants. It is anticipated that a successful intervention would cause some individuals to exceed these goals and some would not improve from baseline. The trial was designed to be able to detect an intervention that results in the following distribution of effects:

- No increase in 25% of subjects
- 1 $\text{kcal} \cdot \text{kg}^{-1} \cdot \text{day}^{-1}$ increase in 25% of participants
- 2 $\text{kcal} \cdot \text{kg}^{-1} \cdot \text{day}^{-1}$ increase in 45% of participants
- 3 $\text{kcal} \cdot \text{kg}^{-1} \cdot \text{day}^{-1}$ increase in 5% of participants

for an average increase of $1.3 \text{ kcal} \cdot \text{kg}^{-1} \cdot \text{day}^{-1}$. The control subjects are assumed to have a distribution of:

- 1 $\text{kcal} \cdot \text{kg}^{-1} \cdot \text{day}^{-1}$ decrease in 10% of control participants
- 0 $\text{kcal} \cdot \text{kg}^{-1} \cdot \text{day}^{-1}$ change in 85% of control participants
- 1 $\text{kcal} \cdot \text{kg}^{-1} \cdot \text{day}^{-1}$ increase in 10% of control participants
- 2 $\text{kcal} \cdot \text{kg}^{-1} \cdot \text{day}^{-1}$ increase in 5% of control participants

for an average increase of $0.2 \text{ kcal} \cdot \text{kg}^{-1} \cdot \text{day}^{-1}$. Based on the above assumptions, it will be necessary to randomize 393 women and 417 men to have 90% power to detect a $1.1 \text{ kcal} \cdot \text{kg}^{-1} \cdot \text{day}^{-1}$ difference in total energy expenditure. These sample sizes will also allow ACT to detect a 7% change in VO_{2max} with approximately 91% power in women and 93% power in men.

5.D. Interim Analysis and Early Stopping

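### C versus B is a primary comparison, but the 1.1 kcal/kg/day difference is argued only against Standard Care; a closed test in 5.A would raise its power without adding participants

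*Protocol*

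**What the plan says.** Section 1.B.1 sets the effects of B and C on each primary outcome at 24 months "when compared to a Standard Care control (Group A) and to each other". Section 5.C carries this through: the hypotheses cover all pairs of groups, "thus a total of six pairwise comparisons will be performed", each at two-sided 0.0083.

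Section 5.A states H1 and H2 as nulls of no difference among the three groups, and "individually, each hypothesis will be tested at significance level 0.025", separately in women and men. It then adds: "Each of the three pairwise comparisons of the intervention groups will be tested using a Bonferroni-adjusted significance level of" 0.0083, that is 0.025/3.

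The design difference is derived in 5.C. One distribution is given for an intervention, averaging +1.3 kcal/kg/day; the text does not say whether this is B or C. A second list follows, introduced by "The control subjects are assumed to have a distribution of", with a stated average of +0.2. The gap is 1.1, and 417 men and 393 women are said to give 90% power to detect it. Elsewhere the protocol describes B as a subset of C that needs less staff time, and sets the participants' goal at an increase of 2 kcal/kg/day or more.

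**The concern.** For B versus A and C versus A, a gap of 1.1 has a rationale in the text. For C versus B it has none, because the comparator is itself an intervention meant to work:

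- If the single +1.3 distribution applies to both arms, the implied C-minus-B difference is zero.
- If B averages +1.3, C must average +2.4 to lead by 1.1.
- If C averages +1.3, it leads by 1.1 only when B does no better than control at +0.2.

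C versus B bears on whether the less resource-intensive model is enough. The protocol gives no help in judging how likely the trial is to separate the two arms. The multiplicity rule also costs power on every pair: it divides 0.025 by three although, with only three groups, a test of the three-group null can do the same protective work.

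**Working it through.** **Inputs (5.C).** Baseline-adjusted SD of energy expenditure 2.0894 (men) and 2.0206 (women); r = 0.8; equal allocation; two-sided level 0.05/6 = 0.0083; z-values 2.64 and 1.282; N = 417 men and 393 women.

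**Reproducing the plan.** N = (1/r) · V · (1/P1 + 1/P2) · (z_alpha + z_beta)² / delta², with 1/P1 + 1/P2 = 6 and delta = 1.1:

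- Men: 1.25 × 2.0894² × 6 × 3.922² / 1.21 = 416.2, or 139 per arm and 417 in all, as stated.
- Women: 1.25 × 2.0206² × 6 × 3.922² / 1.21 = 389.3, or 130 per arm and 390 in all, against a stated 393.

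The plan's sample size therefore holds. VO2max at ln(1.07), with SDs 0.1214 and 0.1215, gives 93.5% in men and 91.8% in women, against the stated 93% and 91%.

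**Power at other differences.** Evaluable per arm: 417 × 0.8 / 3 = 111.2 men and 393 × 0.8 / 3 = 104.8 women. SE = SD × √(2/n) = 0.280 and 0.279. Power = Φ(d/SE − 2.638).

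| True difference d | Men | Women |
|---|---|---|
| 1.10 | 90.1% | 90.4% |
| 0.70 | 44% | 45% |
| 0.60 | 31% | 31% |
| 0.55 | 25% | 25% |

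The 0.55 places B midway between +0.2 and +1.3. The 0.70 takes B at +1.3 and C at exactly 2.0. VO2max at an illustrative 3.5% difference, d = ln(1.035), gives 30% in men and 28% in women.

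**Why the division by three is not needed.** With three groups, any two pairwise nulls together imply the three-group null. The closed family therefore contains only the three-group null and the three pairs. Rejecting a pair when both the three-group test and that pair's test are significant at 0.025 holds familywise error at 0.025 for that outcome and sex. The two outcomes together still spend 0.05.

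**Simulation.** Three-arm normal trials with pooled variance, F test at 0.025 and then t tests at 0.025, against t tests at 0.0083. Power in men (200,000 trials):

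| Means of A, B, C | Pair | 0.0083 rule | Closed |
|---|---|---|---|
| 0.2, 0.75, 1.3 | C−B | 24.6% | 38.5% |
| 0.2, 0.75, 1.3 | C−A | 89.8% | 90.8% |
| 0.2, 1.3, 2.0 | C−B | 44.0% | 59.9% |
| 0.2, 1.3, 2.0 | B−A | 89.7% | 95.3% |

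Runs of 400,000 trials per scenario gave C-versus-B power of 38-39% and 60%. Familywise error was 0.0249 (men) and 0.0254 (women) with all means equal, 0.0251 with B = C, and 0.0246-0.0247 with B = A. All of these equal 0.025 within simulation error.

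**Step-down alternative.** Test the smallest of the three pairwise p-values at 0.0083; if it is rejected, test the other two at 0.025. This rejects everything that the plan's rule rejects, so it can never be less powerful. Familywise error stays at or below about 0.025, C-versus-B power is close to the closed figures, and intervention-versus-A power at 1.1 is about 90-95%.

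**The case against.** The strongest reply is that nothing in the plan is wrong. Section 5.C claims 90% power for a difference of 1.1, its formula is for a generic pair with equal arms and common variance, and the claim is true of C versus B as of any other pair. Every trial has less power for a smaller effect. This stands. A reader might infer that the stated 90% is false for C versus B, or that the plan's own figures imply 25-45%. The documents support neither. The C-minus-B differences are assumptions made here: 0.55 is a midpoint, and 0.70 subtracts an assumed mean from a goal that is stated as at least 2 and that participants are encouraged to exceed. On other readings of the same figures, the difference runs from zero to 1.1.

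The midpoint also depends on the control average. The control proportions add to 10 + 85 + 10 + 5 = 110%, and the listed values give −0.10 + 0 + 0.10 + 0.10 = +0.10, not +0.2. With +0.1, the midpoint difference is 0.60 and power is 31%. The sample size uses 1.1 and does not change.

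Single-step Bonferroni is valid, is used consistently in 5.A and 5.C, and gives simultaneous intervals. The pairwise tests can also be read simply as the way each 0.025 is spent, since 5.A does not make them conditional on a three-group test. That too stands, so the change in procedure is an improvement and not a correction. Nor does it bring C versus B near 90% at these differences.

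A reader might also expect a non-significant C-versus-B result to be taken as equivalence; no section says so. Finally, 5.B allows some secondary analyses with the sexes combined. With 111.2 + 104.8 = 216 per arm and an SD of about 2.06, SE = 2.06 × √(2/216) = 0.198, and power is about 55% at 0.55 and just over 80% at 0.70. This softens the practical consequence but does not alter the primary analysis by sex.

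**Conclusion.** The point holds as a cheap improvement. C versus B is a primary comparison for which 5.C neither assumes nor justifies a difference, and the pairwise rule in 5.A gives up power that three groups do not require it to give up. At the planned size, C must exceed B by 1.1 for 90% power; power is about 25% at 0.55 and 45% at 0.70. The closed procedure moves the last two to about 38-39% and 60%, and intervention-versus-control power at 1.1 from 90% to about 91-95%, with familywise error still about 0.025 per outcome within each sex.

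The power figures rest on the plan's SDs (12-month values for energy expenditure), 20% loss, equal variances and normal theory. The C-minus-B differences are illustrative.

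**What to change.** 1. **Section 5.A.** Within each outcome and sex, test the three-group null at 0.025 and, only if it is rejected, test each pair at 0.025. Alternatively, adopt the step-down rule: smallest pairwise p-value at 0.0083 and, if it is rejected, the other two at 0.025. Name one of the two in advance and align the 0.0083 statement in 5.C with it.
2. **Section 5.C.** Say that the 1.1 rationale is intervention versus Standard Care and that no C-minus-B difference is assumed. Give C-versus-B power at stated illustrative differences, such as 0.55 and 0.70. Reconcile the control distribution with its stated average.
3. **Reporting.** Give C versus B as a difference with its confidence interval.

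The cost is wording only, with no added participants or data. The downsides are small. Pairwise 97.5% intervals are not simultaneous over the three pairs, so 99.17% intervals should be shown alongside. The F-then-t version can occasionally miss a pair that the 0.0083 rule alone would have rejected; the step-down version cannot.

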6. QUALITY CONTROL

6.A. Data Collection

All data collected at the ACT CCs will be gathered by trained and certified staff using standardized procedures, questionnaires and forms. All equipment used for data collection will be routinely calibrated. Reporting forms will be checked for accuracy and completeness prior to the participant leaving the clinic. All staff collecting data will be assigned an ID number that will be used to document who collected each piece of data. Data collected by external sites (e.g., central laboratory) will be transferred electronically to the CCC.

6.B. Reports and Site Visits

Reports generated from the CCC will focus on summarizing: recruitment, screening and enrollment progress, protocol violations, missing/delinquent forms, keying errors, data edits, participant missed visits and participant compliance to the study protocol. Some reports will be issued every 2 weeks (screening/recruitment/enrollment) while others will be prepared and circulated every two to four weeks. Results in these reports will be subclassified by clinical center. No information on study endpoints will be included in these reports. In addition, reports of the intervention process and patient adherence to intervention will be issued.

Site visits to the three clinical sites will occur on an annual basis, with options for additional visits, should the need arise (in instances of poor clinic performance, lagging recruitment, poor quality data, etc.). The purposes of these site visits will be to 1) provide a means for continual training, retraining and reinforcement of standard study procedures, 2) enhance communication between the clinical sites and the CCC, and 3) detect and document the extent of problems in implementing the protocol. Site visits to ACT subcontractors will occur on an "as needed" basis.

7. TRIAL ORGANIZATION

The organizational structure of ACT is shown in Figure 2 (Appendix A). Appendix A also lists participating centers and investigators.

7.A. Clinical Centers (CC)

The Principal Investigator at each CC is responsible for clinic operations and performance. (S)he or co-investigators will actively participate in the protocol and Manual of Procedures development and in the entire recruitment effort, from establishing a system for getting access to participants to informing potential participants about the trial and obtaining informed consent. These investigators will be particularly crucial in recruiting study physicians. They are also responsible for implementing the interventions and follow-up data collection. Close working relationships with the staff are essential to the success of the program. This may include weekly staff meetings. The Principal Investigator and his/her Co-Investigators are also expected to contribute to the conduct and progress of the trial by attending Steering Committee meetings and by serving on and chairing subcommittees and proposing scientific papers and serving on writing teams.

7.B. Clinical Coordinating Center (CCC)

In its role as the Clinical Coordinating Center, Bowman Gray School of Medicine/Wake Forest University (WFU) will perform the following functions in support of the study:

1. develop the study forms and the Manual of Procedures with the guidance of the Steering Committee, Subcommittees, and NHLBI staff;
2. purchase and set up the distributed data entry system;
3. train and certify clinic personnel in the use of the data collection forms and the operation of the microcomputer system for data transmission and management support systems;
4. receive data from all centers, edit the data for errors, and double key a subset of data items;
5. analyze the data;
6. generate regular recruitment and quality control reports to the Steering Committee and Project Office, and in addition to these, endpoint reports for the Data and Safety Monitoring Board (DSMB);
7. serve on study committees;
8. propose papers and assist in the preparation and authorship of papers, including providing statistical support;
9. provide and facilitate communication support among the CCs. It is important that the data coordinators in each CC and the Project Manager at the CCC develop close communications. Electronic mail media will be employed for the transmission of routine messages and for resolution of data problems. Telephone conference calls are also to be used for addressing larger problems; and
10. in collaboration with the Project Office, solicit and select organizations for subcontracts to the CCC for: a Central Lab, and an intervention video. The CCC will monitor the progress and quality control of the subcontracts.

7.C. NHLBI Project Office

The NHLBI Project Office will establish an ACT team consisting of the Project Officer, Deputy Project Officer, Contracting Officer, and other professionals in the NHLBI Division of Epidemiology and Clinical Applications, including a statistician and nutritionist, to perform the following functions:

1. provide direction to the CCs and the CCC regarding budgetary considerations, contracting, and subcontracting, and fund the centers through contracts for each phase of the study;
2. serve on the ACT Steering Committee and subcommittees to contribute to the scientific decisions and conduct of the study;
3. represent NHLBI at Protocol Review Committee and Data Safety Monitoring Board meetings;
4. review data monitoring and other quality control reports;
5. conduct site visits to the CCC and to the CCs on an as needed basis;
6. propose papers and serve on writing groups for publications and presentations;
7. review all ACT manuscripts for publication and abstracts for presentation (approval is required if an NHLBI staff member is a co-author);
8. aid the CCC in soliciting proposals, selecting organizations, and monitoring the progress and quality of work for subcontracts; and

9. provide updates of the status of the study as requested to NHLBI and NIH.

7.D. Steering Committee

The Steering Committee provides the leadership for the study and establishes scientific as well as administrative policy. The Steering Committee will be the main governing body of the trial. The five voting members of the Steering Committee include the Principal Investigators from the CCC and CCs and the NHLBI Project Officer. All major scientific decisions will be determined by consensus or vote of the Steering Committee. Except during the organizational period, the Steering Committee will meet approximately semi-annually.

7.E. Steering Committee Subcommittees

The Steering Committee has appointed subcommittees to make recommendations to the Steering Committee and to conduct major activities of the trial. Designated investigators from the CCC, CCs, and Project Office serve on the subcommittees.

Subcommittees will meet regularly either by conference call or in conjunction with the Steering Committee Meetings. Good cross-site representation on the subcommittees will allow for effective communication between the subcommittees. Subcommittees will report their recommendations to the Steering Committee for consideration. The subcommittees have the following responsibilities:

1. Measurement/Quality Control Subcommittee will:

Define baseline and follow-up outcome data to be collected; determine the means for collecting these data (forms development); determine which data need special monitoring by the CCC (outcomes/events, recruitment, laboratory, etc.); formulate needs for staff training and certification; define coronary heart disease and cardiovascular disease events and methods for reporting them; define potential adverse effects and devise systems to report them; and develop alert values.

2. Design & Analysis/Publications & Presentations Subcommittee will:

Develop recommendations for the major aspects of study design, including the definition of outcome measures, sample size, randomization strategies and analysis plans; review and approve all trial-related publications, presentations and ancillary studies; and ensure fair site representation, as well as high quality reporting and timeliness for all publications and presentations.

3. Intervention Subcommittee will:

Formulate the content and approach for the trial interventions; devise systems to monitor them; and develop measures to follow participant and staff adherence to intervention delivery and receipt.

4. Recruitment/Eligibility Subcommittee will:

Develop eligibility criteria; determine what data will be collected during trial screening; formulate viable recruitment strategies; develop the informed consent; and monitor retention during follow-up.

5. Trial Coordinator Subcommittee will:

Discuss implementation of the Manual of Procedures and the impact of protocol changes, ancillary studies, etc. on clinic operations (participant flow, data collection, recruitment, compliance, etc.); propose streamlining procedures that would facilitate clinic operations and data collection efforts; collaborate with the Measurement/Quality Control Subcommittee on staff training, certification and recertification needs.

7.F. Protocol Review Committee (PRC)/Data and Safety Monitoring Board (DSMB)

The PRC/DSMB is appointed by the NHLBI and advises the NHLBI on the conduct of the study. The PRC/DSMB consists of a non-trial chairperson and additional non-trial voting members appointed by the NHLBI. The PRC/DSMB meetings will be attended by the NHLBI Project Office and the PI of the CCC, and the Steering Committee Chair. The PRC will make a formal recommendation to the NHLBI regarding whether the study protocol should be implemented. Meetings of the DSMB (either face-to-face or conference calls) will be held two times per year. Specific responsibilities of the DSMB include:

1. conducting reviews on the progress of the trial, including evaluating participant recruitment and compliance to the protocol;
2. reviewing and approving any subsequent changes to the protocol;
3. reviewing outcome data and making recommendations to the NHLBI on continuation of the study and possible termination, should it become necessary to protect the safety and welfare of the participants; and
4. assisting the NHLBI in resolving problems referred by the Principal Investigators.

7.G. Clinical Coordinating Center Subcontracts

1. Central Blood Laboratory:

A Central Blood Laboratory will be used to analyze the fasting lipid profile (total cholesterol, triglycerides, HDL and calculated LDL), fasting plasma insulin, and fibrinogen levels. Employment of the Central Laboratory should reduce analytical variance and permit convenient performance monitoring and (if required) remediation. Preparation, storage and shipping of blood samples will be performed according to a standard protocol. Detailed instructions on all aspects of collection, processing and shipping will be written into the ACT Manual of Procedures.

2. Video Subcontractor:

The video subcontractor to the CCC represents a short-term (during the ACT planning phase) cost reimbursement subcontract to develop and implement a 15-20 minute video that will serve as part of Interventions B and C. The subcontractor will collaborate with the

ACT CCC, the NHLBI Project Office and the ACT Intervention Subcommittee to develop, produce, test, adapt and implement the video that will be based on behavioral principles promoting initiation and maintenance of physical activity.

7.H. Publications & Presentations Policy Objectives

The ACT Publications and Presentations policy is in Appendix C. The objectives of the publications and presentations editorial policy are to assure and uphold:

- Expeditious and timely dissemination to the scientific community of all pertinent data resulting from ACT;
- Accurate and scientifically sound publications and presentations from ACT and its collaborating investigators;
- Promotion of and encouragement for analysis and submission of manuscripts among the ACT investigators;
- Establishment of a system for fair determination of authorship on ACT collaborative publications;
- That investigators from all participating ACT centers, particularly those of junior faculty rank and other junior investigators, have the opportunity to participate and be recognized in studywide publications and presentations;
- That press releases, interviews, promotional materials and other circulated ACT documents are accurate and objective, and do not compromise the collaborative trial and the acceptance of its results; and
- Establishment of procedures that allow the NHLBI to review in a timely fashion publications and presentations summarizing data collected during the course of the trial.

7.I. Ancillary Studies

1. General Policy:

ACT investigators are encouraged to propose and conduct ancillary studies. Such studies enhance the value of ACT and ensure the continued interest of the diverse group of investigators who are critical to the success of the study. To protect the integrity of ACT, ancillary studies must be reviewed and recommended by the Design and Analysis (D&A) Subcommittee and approved by the Steering Committee before their initiation. By definition, ancillary studies will require outside (non-ACT) funding.

2. Definition:

An ancillary study is one based upon information from ACT participants in an investigation which is not described in the ACT protocol and involves additional data which are not collected as part of the routine ACT data set, or additional biologic specimens for analysis or storage. Separate informed consent must be obtained from all ancillary study participants, and should clearly identify the ancillary study as one being performed in addition to the main study. An ancillary study may also use ACT data in the analysis (e.g., demographic information, medication use, etc.). An ACT principal investigator or co-investigator must be included as a co-investigator in every ancillary study proposal, to promote continuity with ACT. An investigator from the ACT CCC should be included as an investigator in every

Connect the "Summary of ACT P&P Policies" which is located directly behind the protocol.

(P+P)

ancillary study proposal to ensure the necessary access to the database and to facilitate data analyses, unless the CCC deems this unnecessary.

3. Approval Process:

The Design and Analysis (D&A) Subcommittee will be responsible for initial review of ancillary study proposals. Investigators will provide a three to six page summary of the proposed ancillary study to the D & A Subcommittee, which will discuss the proposal in light of the following approval criteria. (Before an ancillary study can be approved, it must be demonstrated that the ancillary study will have scientific merit and will not unduly:

- a. interfere with the completion of the main objectives of ACT or complicate interpretation of the ACT results;
- b. result in unmasking of staff assessing study outcomes;
- c. adversely affect participant burden or cooperation in ACT; or
- d. jeopardize the public image of ACT.

4. Publications resulting from ancillary studies will follow the same policies as described in the ACT Publication and Presentation Policy (Appendix C), except that the writing committee will be determined by the ancillary study investigators. *

Consult
APP D for
details of policy.

